5.4. REPORTING / RECORDING OF SAEs

5.4.1. INVESTIGATOR'S RESPONSIBILITY

SAEs will be recorded following the first study drug administration through the 9 month follow-up visit. Any serious adverse event that occurs during this investigation, whether or not related to the study medication, must be reported immediately (within 72 hours) to the Sponsor and MedTech Consultants, Inc., the designated CRO.

Each SAE must be followed with appropriate medical management until resolved or assessed as chronic or stable regardless of whether or not, in the opinion of the Investigator, the event is thought to be related to the study medication.

The Investigator will be required to provide complete information concerning each SAE to the CRO and Sponsor within 5 calendar days of the event. This information must be recorded in the subject's medical record and then transcribed onto the SAE Form. The completed SAE Form (including the Investigator's opinion of the relationship of the SAE to the study medication), copies of related results/reports, consultant report(s), and other relevant information will be faxed and mailed to the CRO.

In the event of an SAE leading to hospitalization, every effort will be made by the investigational site to obtain medical records, including a hospital discharge summary. In the event of a fatal AE, documentation of any available postmortem findings, including autopsy, will be provided to the Sponsor or their designee. In any event, the Investigator will provide a narrative summary of circumstances,

events related to the death, and cause of death, if known. Any follow-up information obtained must be recorded on an SAE follow-up report form.

The Investigator must comply with the applicable local regulatory requirements related to the reporting of SAEs to regulatory authorities and the Institutional Review Board (IRB), and Institutional Biosafety Committee (IBC) if applicable. Upon receipt from the Sponsor of an initial or follow-up IND Safety Report or other safety information, the Investigator must promptly notify his or her IRB, and IBC (if applicable).

5.4.2. SPONSOR'S RESPONSIBILITY

All AEs and SAEs will be reported on an annual basis to FDA in accordance with the IND regulation (21 CFR Part 312). Per the 2010 FDA Guidance Document for Industry and Investigators “Safety Reporting Requirements for INDs and BA/BE Studies,” events categorized as ‘possibly’ or ‘probably’ related will be treated as ‘suspected adverse reactions.’ Events categorized as ‘definitely’ related will be treated as an ‘adverse reaction.’

All serious, unexpected adverse reactions and suspected adverse reactions will be reported to FDA and to all participating investigators as an IND Safety Report within 15 calendar days of the event after the sponsor determines that the suspected adverse reaction qualifies for reporting (21 CFR §312.32). Any unexpected fatal or life-threatening AEs will be reported to the Agency within 7 calendar days after the sponsor’s initial receipt of the information.

The Sponsor will notify all participating investigators of any new safety information that alters the current risk-benefit assessment of the study medication or that would be sufficient to consider changes in VM202 administration or in the overall conduct of the trial.

6. STATISTICAL METHODS

The objective of this Phase II study is to evaluate the safety of IM administration of VM202 in subjects with painful DPN in lower extremities; and, to evaluate the potential bioactivity of IM administration of VM202 in subjects with painful DPN, when compared to placebo, on rest pain (as assessed by frequency of pain, pain medication use history, sleeping history, and intensity of pain) and sensory perception.

6.1. GENERAL METHODS

Means, standard deviations (SD), medians and minimum and maximums will be presented for continuous variables, the number and percentage of patients in each category will be presented for nominal and ordered categorical variables. Statistical tests with a p value <0.05 will be considered statistically significant, unless otherwise stated.

6.2. ANALYSIS POPULATION

Efficacy Analysis Population – Subjects that received all injections of the correct dose of study drug medication based on randomization schedule and have completed the 6-month assessment; subjects must not have any protocol violation or major deviation which will be determined in a blinded review before database lock for data analyses.

Safety Analysis Population – Subjects that have received any injections

Intent to Treat (ITT) Population – All randomized patients

6.3. STUDY ENDPOINTS

The objectives of this study are to evaluate the safety of IM administration of VM202 in subjects with painful DPN in lower extremities; and to evaluate the potential bioactivity of IM administration of VM202 in subjects with painful DPN, when compared with placebo, on pain.

6.3.1. PRIMARY ENDPOINT

The primary study endpoint is the change in average 24-hour pain score from baseline to the 6-month follow-up. The average pain scores will be obtained from the Daily Pain and Sleep Interference Diary (recorded daily by the patient for 7 days prior to the first round of injections and again, for 7 days before the 6 month follow-up). The difference in the mean change in average 24 hour pain score between the two treatment groups and the placebo arm will be evaluated to determine the treatment effect.

The primary analysis will be conducted in the Efficacy Analysis Group. A secondary analysis will be conducted in the ITT group, and further analyses conducted as necessary to explore any inconsistency between the two results.

6.3.2. SECONDARY EFFICACY ENDPOINTS

Other secondary endpoints and evaluations will include:

- Difference in all clinical parameters measured (VAS, BPI DPN, MNSI, PGIC, average pain score and sleep interference score from the Daily Pain and Sleep Interference Diary) and histological findings on skin biopsy between the low dose and high dose groups at all time points
- Change between treatment arms and placebo in VAS score from baseline to Day 30, Day 60, Day 90, 6 months, and 9 months.
- Change in mean pain score from the Daily Pain and Sleep Interference Diary between treatment arms and placebo from baseline to Day 90, 6 months and 9 months.
- Change between treatment arms and placebo in mean MNSI score from baseline to 6 months and 9 months.
- Change between treatment arms and placebo in BPI-DPN from baseline to Day 30, Day 60, Day 90, 6 months, and 9 months.

- Change in PGIC between treatment arms and placebo at Day 30, Day 60, Day 90, 6 months, and 9 months.
- Change between treatment arms and placebo in histological findings on skin biopsy from baseline to 6 months

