1.6.3. PHASE I/II STUDY IN PATIENTS WITH PAINFUL DPN

VM202 was evaluated for treatment of DPN in an ongoing prospective, dose-escalation Phase I study. The study consisted of three (3) cohorts of four (4) subjects. Subjects received 4 mg, 8 mg, or 16 mg VM202 unilaterally in a calf. For each dose cohort, VM202 was administered as local intramuscular injections with half of the dose administered at Day 0 of the study and the second half administered

2 weeks later. Preliminary efficacy (hemodynamic assessments), safety and tolerability were evaluated at Baseline (screening) and at designated time points throughout the study. All 3 dose cohorts were followed for one year from the time of the first dose of study drug administration. Between June 2010 and March 2011, twelve (12) subjects were enrolled in the study, and enrollment and follow-up are complete.

Ten out of 12 subjects (10/12, 83%) experienced a reduction in pain at their 6 month visit. One patient each in Cohort I and Cohort II did not experience a reduction in pain. At 6 month, mean change in VAS was -8.2 in Cohort I, -31.6 in Cohort II and -25 in Cohort III.

At 12 month, 9 out of 12 subjects (9/12, 75%) experienced a reduction in pain. The same 2 patients, one each in Cohort I and Cohort II did not experience a reduction in pain, and one patient in Cohort III returned to baseline levels at 12 month. At 12 month, mean change in VAS was -12.0 in Cohort I, -32.8 in Cohort II and -18.5 in Cohort III. VAS scores also tracked well with other quality of life measures (BPI-DPN).

Intramuscular injections of VM202 appear to be well tolerated at doses as high as 16 mg in patients with DPN. There were no incidents of dose limiting toxicities (DLT). There have been no serious or unexpected adverse events in the study. The level of VM202 DNA was below the LLOQ in all 12 subjects by day 90. Circulating HGF levels remained relatively constant throughout the study, suggesting that the plasmid remained active only at the injection site.

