4. SAMPLE SIZE JUSTIFICATION

The sample size for this Phase 2 study was chosen to estimate effect sizes and variability for a pivotal study. Based on the 12 subjects in the Phase I study (Protocol VMDN-001), the overall mean VAS reduction from baseline to 6 months is about 23 mm with a standard deviation of about 25 mm.

This Phase II study has two VM202 dose groups (16 mg and 32 mg) and a placebo group. The study goal is to identify any difference in mean reduction in pain as measured by the Daily Pain and Sleep Interference Diary between each of the two VM202 groups against the placebo group. Based on the two-sided two-sample t-test with a significance level of 0.025 (per the Bonferroni adjustment for multiple comparisons) and an assumption of a standard deviation of 25 mm, a sample size of 40 subjects versus 20 subjects has a statistical power of 80% to detect a mean difference of 21.5 mm, a statistical power of 70% to detect a mean difference 19.5 mm, and a statistical power of 60% to detect a mean difference of 17.5 mm. Therefore, the sample size for Protocol VMDN-002 is determined to be 40 subjects in the VM202 16 mg group, 40 subjects in the VM202 32 mg group, and 20 subjects in the placebo group.

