5.2. Statistical Methods

Although the detectable effect size for the mean pain score reduction is calculated by the two-sided t-test with a significance level of 0.025 per Bonferroni adjustment, the Analysis of Variance (ANOVA) will be performed to detect any difference in the 6-month mean pain score reduction (as measured using the Daily Pain and Sleep Interference Diary) among the three study groups first and, if there is a significant findings based on ANOVA,

the Dunnett's test for the multiple comparisons will be used to compare each of the two VM202 groups and the placebo group in the 6-month mean pain score. Therefore, two-sided p-values <0.05 will be considered statistically significant, unless otherwise stated. As described previously, regardless of the statistical significance, the p-values of the statistical tests should be used descriptively with clinically meaningful interpretation.

Separate statistical tests will be performed at each time point for key endpoints of interest such as Visual Analogue Scale for Pain, Brief Pain Inventory for Diabetic Peripheral Neuropathy, Michigan Neuropathy Screening Instrument, Patients' Global Impression Change, and the [REDACTED] No adjustment for multiplicity will be performed.

In general, an overall test to determine if there is a statistically significant difference among the three treatment arms will be conducted first. Further comparisons will be made to determine if either the low or high dose groups are statistically significantly different from the placebo group.

For continuous variables, a one-way analysis of variance (ANOVA) with treatment group (high dose, low dose, and placebo) as a factor will be used to determine if there is a significant difference among the groups. The low and high dose groups will each be compared against the placebo group using Dunnett's test. The mean difference between the VM202 groups versus placebo along with 95% confidence intervals for the mean difference will also be presented.

For categorical variables, Fisher's exact test will be used to determine if there is a significant difference among the three treatment groups. Separate Fisher's exact tests will be used to compare the low and high dose groups to the placebo group.

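### The SAP does not pre-specify the low versus high dose contrast that Protocol 6.3.2 lists as a secondary endpoint; all its pairwise tests and intervals are against placebo.

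*Protocol*

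**What the plan says.** Protocol 6.3.2 gives the secondary efficacy endpoints as an unranked list of bullets. The first is the difference "between the low dose and high dose groups at all time points" in VAS, BPI-DPN, MNSI, PGIC, diary pain, diary sleep interference and skin-biopsy histology. The remaining bullets compare the treatment arms with placebo, so the dose contrast is a separate commitment.

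The SAP compares pairs only against placebo:

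- Section 2.2 (objectives) compares the VM202 groups with placebo, and section 4 states the goal as each dose against placebo.
- Section 5.2 has an overall three-group test and then, for continuous variables, "The low and high dose groups will each be compared against the placebo group using" Dunnett's test. The intervals for mean differences are VM202 versus placebo. Fisher's exact test follows the same pattern for categorical variables.
- Sections 11.1 (primary endpoint) and 11.2 (responders) repeat that structure.
- Sections 11.3.1 to 11.3.5 (VAS, BPI-DPN, MNSI, PGIC, sleep interference) refer back to the method for continuous variables.
- Appendix A lists no table for a dose contrast.

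Section 5 does provide means, standard deviations, medians, minimums and maximums for each arm. Sections 2.2 and 12.5 leave the histology to an independent laboratory's report and do not describe its comparisons.

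**The concern.** If the SAP is followed exactly, a listed secondary endpoint is reported with neither an estimate nor an interval. The SAP does not say that the endpoint was dropped.

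The two placebo comparisons cannot stand in for it. They share the same 20 placebo subjects, and finding one dose significant and the other not is no evidence that the doses differ. The overall ANOVA has both dose means in its null hypothesis but does not isolate their difference.

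The SAP says the study serves the planning of Phase III (section 5) and was sized to estimate effect sizes and variability for a pivotal study (section 4). That such planning includes weighing two doses is an inference, though a modest one for a trial with two active arms. Protocol 1.6.3 shows the question is not closed: at 6 months "mean change in VAS was -8.2 in Cohort I, -31.6 in Cohort II and -25 in Cohort III". If someone computes the dose difference after unblinding, it is a post hoc analysis of an endpoint that the protocol had already named. SAP section 1 requires departures from the plan to be documented in the study report.

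**Working it through.** **Inputs.** Arm sizes 40, 40 and 20 (SAP section 4). SD from the same section: "an assumption of a standard deviation of 25 mm". Test: two-sided two-sample t-test at 0.025, the Bonferroni level. Phase I cohort means at 6 months: Protocol 1.6.3.

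**Step 1: reproduce the SAP's own figures.** SAP section 4 states that "a sample size of 40 subjects versus 20 subjects has a statistical power of 80% to detect a mean difference of 21.5 mm". It also gives 70% at 19.5 mm and 60% at 17.5 mm. The standard error for 40 v 20 is 25 × √(1/40 + 1/20) = 6.85 mm. The noncentral t with 58 degrees of freedom gives:

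| Difference | SAP power | Recomputed |
|---|---|---|
| 21.5 mm | 80% | 79.7% |
| 19.5 mm | 70% | 70.7% |
| 17.5 mm | 60% | 60.2% |

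The figures reproduce. They cover dose versus placebo only; the SAP gives none for low versus high.

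**Step 2: precision of the missing contrast.** Half-width = t × SD × √(1/n₁ + 1/n₂). With the pooled ANOVA variance, df = 100 − 3 = 97 and t = 1.985.

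- High v low (40 v 40): SE = 25 × √(1/40 + 1/40) = 5.59 mm; half-width = 1.985 × 5.59 = 11.1 mm.
- Dose v placebo (40 v 20), unadjusted: 1.985 × 6.85 = 13.6 mm.
- Dose v placebo, Dunnett critical value 2.218: 2.218 × 6.85 = 15.2 mm.

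In SD units the standard errors are 0.224 and 0.274, so the omitted contrast is the most precise pairwise comparison in the trial.

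**Step 3: losses.** The primary analysis uses the Efficacy Analysis Group, which excludes subjects without a 6-month assessment and those with violations. No loss rate is stated. Assuming 10% or 20% loss:

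- 36 v 36: SE 5.89 mm, half-width about 11.7 mm.
- 32 v 32: SE 6.25 mm, half-width about 12.4–12.5 mm.

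**Step 4: the diary scale.** The 25 mm SD comes from the Phase I VAS, while the diary runs from 0 to 10. Reading 25 mm as 2.5 points is an assumption that the SAP does not state. Unadjusted half-widths (97 df):

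| Assumed diary SD | High v low | Dose v placebo |
|---|---|---|
| 2.0 points | 0.89 | 1.09 |
| 2.5 points | 1.11 | 1.36 |
| 3.0 points | 1.33 | 1.63 |

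**Step 5: what the contrast could resolve.** The gap between Cohorts II and III is 31.6 − 25 = 6.6 mm. With 40 v 40, SD 25 mm and two-sided 0.05, power is about 21–22%. The difference detectable with 80% power is 15.9 mm. The Phase I gap itself comes from four subjects per cohort: its SE at the same SD is 25 × √(1/4 + 1/4) = 17.7 mm.

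**The case against.** The strongest reply is that nothing is lost. The SAP reports means and SDs by arm, scores by visit and arm, and responder percentages by arm. The point estimate follows by subtraction, and an approximate interval from the SDs and Ns. A reader might infer that the trial would fail to estimate the dose difference at all; the documents do not support that. What is missing is a pre-specified, displayed contrast with its interval, and that much of the concern stands.

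Four further limits also stand:

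- A reader might infer that the documents make the dose difference a requirement for Phase III. They give a general planning purpose and never name it; the objectives are safety and bioactivity against placebo.
- Being the first bullet gives the endpoint no priority, because the list is unranked.
- It would be too broad to say that no endpoint will receive this comparison. The laboratory's histology report is undescribed, so a dose contrast there is unspecified, not shown to be absent.
- The Phase I figures are weak evidence of a non-monotonic response. They rest on four subjects per cohort, treated in one calf, and matching Cohorts II and III to 8 and 16 mg per leg relies on listing order.

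One could add that p-values are declared descriptive and the contrast is underpowered, so the omission changes no primary conclusion. That is true, but it argues for labelling the contrast descriptive. It does not explain why the SAP's placebo-only rule leaves out a listed endpoint.

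**Conclusion.** The gap between protocol and SAP is real. Protocol 6.3.2 names the low versus high dose difference, and the SAP's pairwise rule does not deliver it for the clinical measures. It should be corrected before unblinding. The primary analysis, its type I error and the safety conclusions are unaffected.

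The contrast would be tighter than either placebo comparison: about 11.1 mm against 13.6 mm (15.2 mm by Dunnett), or 11.7–12.5 mm with 10–20% loss. It would still be too wide to resolve a difference like the 6.6 mm seen in Phase I. It therefore informs dose choice without settling it. These figures rest on the SAP's 25 mm SD, on full 40/40/20 enrolment except where losses are shown, and on assumed loss rates.

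**What to change.** Add to SAP 5.2, 11.1 and 11.3 the high-minus-low mean difference with an unadjusted 95% confidence interval, from the same one-way ANOVA, at each visit where the measure is taken. It should cover diary pain, sleep interference, VAS, BPI-DPN, MNSI and PGIC. Label it descriptive and state that the trial is not powered for it. Ask that the independent laboratory's histology report include the same contrast. A responder contrast in 11.2 is optional, since the protocol bullet does not list responders.

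The cost is a few sentences in the SAP and one more column per efficacy table. No new data are needed and the primary test does not change. The downside is one more unadjusted comparison per endpoint, in a plan that already makes no multiplicity adjustment for these endpoints (SAP 5.2 and 11.4).

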6.3.3. SAFETY

Any patient who receives injections (study drug or placebo) will be included in the safety analysis population. Adverse events (including serious adverse events, and adverse events leading to treatment discontinuation) throughout the 9 month follow-up will be described according to severity and to their relationship with the study drug and injection procedure. Descriptive statistics (N, mean, median, SD, minimum and maximum values, where applicable) will be used to characterize safety parameters.

6.3.4. PHARMACODYNAMICS

HGF serum levels will be determined immediately pre-treatment on Day 0, immediately pre-treatment on Day 14, on Day 30, Day 60, and Day 90. Copies of VM202 in whole blood will be determined at Day 0 (pre-injection and 2 hours post injection), at Day 14 (pre-injection and 2 hours post injection), Day 21, Day 30, Day 60 and Day 90.

6.3.5. DATA SAFETY MONITORING AND INTERIM ANALYSES

For ethical reasons, and to ensure study integrity, an interim examination of key safety data will be performed when approximately 50% of the patients (n=50) have Day 90 data. The primary objective of this analysis will be to evaluate the accumulating data for an unacceptably high frequency of negative clinical outcomes in either active treatment arm. An independent data safety monitoring board (DSMB) will perform the review.

The DSMB Chair will review a limited set of unblinded tables and listings, including all reported AEs and SAEs, every three months through to the full DSMB interim analysis and continue the review every six months thereafter. The DSMB chair may request additional data for review and/or additional meetings of the committee as he / she sees fit.

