POPULATION	Subjects aged ≥ 18 years to ≤ 75 years diagnosed with painful diabetic neuropathy in both lower extremities.
STUDY DESIGN	A phase II, double-blind, randomized, placebo-controlled, multicenter, 9-month study designed to assess the safety and efficacy of bilateral intramuscular (IM) injection of VM202 in the calf of subjects with painful diabetic peripheral neuropathy (DPN). One-hundred (100) subjects will be randomized in a 2:2:1 ratio to one of three treatment groups: Low Dose: 16 mg VM202 - 40 subjects High Dose: 32 mg VM202 - 40 subjects Control – Placebo (normal saline) - 20 subjects Up to twenty (20) sites will participate in the study. Safety will be monitored throughout the study and assessed by an independent Data Safety Monitoring Board (DSMB).
STUDY OBJECTIVES	
• To evaluate the safety of IM administration of VM202 in subjects with painful DPN in lower extremities.• To evaluate the potential bioactivity of IM administration of VM202 in subjects with painful DPN, when compared with placebo, on pain.
INCLUSION CRITERIA	
1. Age ≥ 18 years to ≤ 75 years;2. Documented history of Type I or II diabetes with current treatment control (glycosylated hemoglobin A_{1c} of $\leq 10.0\%$ at

Screening) and currently on oral medication and / or insulin

3. Diagnosis of painful diabetic peripheral neuropathy in both lower extremities;
4. Lower extremity pain for at least 6 months
5. Visual analog scale (VAS) score of ≥ 40 mm at Initial Screening (0 mm = no pain – 100 mm very severe pain);
6. Symptoms from the Brief Pain Neuropathy Screening (BPNS) is ≤ 5 point difference between legs at Initial Screening;
7. The average daily pain intensity score of the Daily Pain and Sleep Interference Diary completed after medication wash-out is ≥ 4 with a standard deviation ≤ 2 ;
8. The physical examination component of the Michigan Neuropathy Screening Instrument Score (MNSI) is ≥ 3 at Screening;
9. Stable treatment of diabetes for at least 3 months with no anticipated changes in medication regimen, and no new symptoms associated with diabetes; and
10. If female of childbearing potential, negative urine pregnancy test at screening and using acceptable method of birth control during the study.

EXCLUSION CRITERIA

1. Peripheral neuropathy caused by condition other than diabetes;
2. Other pain more severe than neuropathic pain that would prevent assessment of DPN;

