1.7. STUDY AND DOSE RATIONALE

DPN, by definition, is a bilateral neuropathy. Treating only one leg may confound patient-reported pain levels and quality of life measures. Based on the excellent safety profile of VM202 seen thus far in the phase I CLI study, the ongoing phase II CLI study and the safety and preliminary efficacy data from the phase I/II study of VM202 injections in patients with DPN, we propose bilateral treatment in this phase II study.

Two doses of VM202 will be tested against placebo (normal saline). The dose of VM202 per leg will remain within the dosing scheme of the phase I/II study (8 mg / leg and 16 mg /leg), and the same dosing schedule used in the DPN phase I study will be followed in this study (namely, intramuscular injections in the calf will be

given on Day 0, and Day 14). As in all three prior studies, VM202 will be delivered in a solution of 0.5 mg VM202 / mL. Subjects will be treated with an overall final dose of 16 mg VM202, 32 mg VM202 or placebo, dosages well within those supported by the body of pharmacology and toxicology safety studies of VM202. Safety studies in rabbit, rat and mouse models demonstrate that doses approximately 2½ (80mg/70kg) to 30 (960mg/70kg) times the maximum clinical dose (32 mg) proposed in this study are safe and resulted in no toxicities.

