12.9. Interim Analyses

An independent data safety monitoring board (DSMB) will review a limited set of un-blinded tables and listings, including all reported SAEs. There will be no adjustment for multiple testing because the results of the interim analysis will not be used to declare the study a success, the unblinded analyses will be performed by a person independent to the study project statistician, and the detailed unblinded findings will not be shared with the project team.

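### After the full-board look at 50 subjects, the scheduled unblinded safety review slows from three-monthly to six-monthly, although subjects may still be receiving injections

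*Protocol*

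**What the plan says.** The Protocol synopsis sets the size and allocation: "One-hundred (100) subjects will be randomized in a 2:2:1 ratio to one of three treatment groups". Each subject is injected on Day 0 and Day 14 only. Up to twenty sites take part.

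Protocol 6.3.5 sets two layers of safety review:

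- The full DSMB examines key safety data "when approximately 50% of the patients (n=50) have Day 90 data". The stated aim is to detect too many bad outcomes in either active arm.
- Around that look there is a periodic review by one member: "The DSMB Chair will review a limited set of unblinded tables and listings, including all reported AEs and SAEs". Its timing is "every three months through to the full DSMB interim analysis and continue the review every six months thereafter".

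The same section adds a discretionary power: "The DSMB chair may request additional data for review and/or additional meetings of the committee as he / she sees fit". It states no trigger for using it.

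SAP 12.9 says that the DSMB "will review a limited set of un-blinded tables and listings, including all reported SAEs". It gives no frequency and does not name non-serious AEs.

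Neither document gives an accrual rate, a pause in enrolment at the full-board look, or a link between review frequency and the end of dosing.

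**The concern.** A review can change what happens to a subject's injections only if it comes before them. Dosing is over by Day 14, while the full-board look waits for Day 90 data on the first 50. More subjects are dosed in those three months, and the rest after the look. The scheduled interval doubles just as that last group begins treatment.

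The by-arm frequency of adverse events is at stake. Investigators, study monitors and the study manager are blinded (Protocol 3.4.6), so an imbalance between arms in non-serious events is scheduled to be seen unblinded only at these reviews. If the next one comes after the last injection, it can no longer affect anyone's dosing.

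**Working it through.** **The plan's own figure.** 50% of 100 subjects = 0.50 × 100 = 50, as Protocol 6.3.5 states.

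**Inputs from the documents.** 100 subjects (synopsis); full-board look at 50 with Day 90 data; review interval of 3 months before it and 6 months after (6.3.5); doses on Day 0 and Day 14.

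**Assumptions.** Subjects start treatment at a constant rate of r per month. Enrolment does not pause. The look takes place as soon as the 50th subject reaches Day 90, and the next Chair review follows one full interval later. Day 90 is taken as 3 months.

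**Formulas.**

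- Time of the look: 50/r + 3 months.
- First-dosed by then: 50 + 3r. Undosed: 50 − 3r.
- First-dosed before the next review: min(50 − 3r, 6r) with the planned interval; min(50 − 3r, 3r) if it stayed at three months.

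| r per month | Dosed at the look | Undosed at the look | Dosed before next review, six-monthly | Dosed before next review, three-monthly |
|---|---|---|---|---|
| 3 | 59 | 41 | 18 | 9 |
| 4 | 62 | 38 | 24 | 12 |
| 5 | 65 | 35 | 30 | 15 |
| 6 | 68 | 32 | 32 | 18 |
| 8 | 74 | 26 | 26 | 24 |
| 10 | 80 | 20 | 20 | 20 |

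**Thresholds.**

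- Six-monthly: nobody is undosed at the next review once 6r ≥ 50 − 3r, so r ≥ 50/9 = 5.6.
- Three-monthly: the same happens once 3r ≥ 50 − 3r, so r ≥ 50/6 = 8.3.
- Nobody is left to dose at the look itself once 3r ≥ 50, so r ≥ 50/3 = 16.7.

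The interval thus changes the number dosed before the next review at every rate below about 8.3. It decides whether anyone at all is still undosed only between about 5.6 and 8.3. At r = 6 the difference is 32 − 18 = 14 subjects, of whom 14 × 4/5 ≈ 11 would be on active treatment under 2:2:1 allocation.

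**Sensitivity.** With 90 days taken as 2.96 months, the two thresholds are 5.6 and 8.4 for the first dose, and 5.9 and 9.1 for both doses. A one-month lag before the look lowers the first-dose thresholds to 5.0 and 7.2. If 10% of subjects are replaced (110 treated, look after 55), they rise to 6.1 and 9.2. The pattern is the same throughout.

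**The case against.** The strongest reply is that everyone dosed after the look is dosed after a full-board, unblinded review of about 50 subjects with Day 90 data, preceded by three-monthly Chair reviews. Reviewing less often after a clean look is a legitimate choice. Other protections also continue: SAEs go to the sponsor within 72 hours (5.4.1), serious unexpected suspected reactions go to FDA and all investigators within 15 days (5.4.2), the sponsor may stop the study for safety (3.5.3), and the Chair may ask for more. All of this stands. What it does not supply is a scheduled by-arm view of events in the subjects dosed after the look. Expedited reports concern individual serious events, and the Chair's power has no stated trigger.

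A reader might also infer four stronger things that the documents do not support.

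- *That at about 6 per month or more the slowing causes all remaining subjects to be dosed unreviewed.* The rate is not in the documents. Above about 8.3 per month the three-monthly schedule gives the same result. And these subjects follow a full-board review.
- *That the whole second half is treated under the sparser schedule.* At 4 to 10 per month, 12 to 30 of the second 50 (3r) are dosed before the look. The affected group is the other 38 to 20.
- *That the SAP withholds non-serious reactions from the DSMB.* SAP 12.9 introduces SAEs with a word that does not make the list exhaustive, and Protocol 6.3.5 expressly covers all AEs. This is a mismatch to align, not an omission shown.
- *That the high dose is untested because it doubles earlier exposure.* The earlier DPN study concludes "Intramuscular injections of VM202 appear to be well tolerated at doses as high as 16 mg in patients with DPN", whereas here "Subjects will be treated with an overall final dose of 16 mg VM202, 32 mg VM202 or placebo". The per-patient total of 32 mg is indeed twice 16 mg. But that study treated one calf and this one treats both, and Protocol 1.7 notes that the per-leg dose stays within the earlier range.

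**Conclusion.** The point holds as a modest, low-cost improvement to safety monitoring. It does not show that subjects go unprotected. The lengthening of the interval is plain in Protocol 6.3.5, and no provision keeps the shorter interval while dosing continues.

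Its size depends on an accrual rate that the documents do not give. At 4 per month the planned interval doubles the number dosed before the next scheduled review, from 12 to 24 of 38. At 6 it raises it from 18 to all 32. At 10 it changes nothing. For scale, 6 per month over 20 sites is 0.3 per site per month. The result rests on constant accrual, no pause and a prompt look, and it concerns scheduled reviews only.

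**What to change.** In Protocol 6.3.5, change the interval after the full-board look to: *every three months until the last subject has Day 90 data, then every six months*. In SAP 12.9, name all AEs and SAEs, with injection-site reaction grades, by arm, so that it matches Protocol 6.3.5.

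**Cost.** From the look to the last subject's Day 90 takes (100/r + 3) − (50/r + 3) = 50/r months. At r = 3 that is 16.7 months: five three-monthly reviews instead of two, so three extra. At r = 4 it is 12.5 months: four instead of two. At r = 6 it is 8.3 months: two instead of one. At r = 10 it is 5 months: one instead of none. The price is therefore about one to three extra runs of existing unblinded tables and Chair reviews, plus the wording changes.

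Leave the full-board look at Day 90. Bringing it forward, for example to Day 30 data, would shorten follow-up per subject at that look and leave more subjects to be dosed after it. That is a trade-off, not a clear gain.
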